	Grade 3 or 4 (Grade 3: severe symptoms; limiting self-care ADL; oxygen indicated) (Grade 4: life-threatening respiratory compromise; urgent intervention indicated [e.g., tracheostomy or intubation])	Permanently discontinue study drug/study regimen.	For Grade 3 or 4 (severe or new symptoms, new/worsening hypoxia, life-threatening): 
 – Promptly initiate empiric IV methylprednisolone 1 to 4 mg/kg/day or equivalent. – Obtain Pulmonary and Infectious disease consult; consider, as necessary, discussing with study physician. – Hospitalize the patient. – Supportive care (e.g., oxygen). – If no improvement within 3 to 5 days, additional workup should be considered and prompt treatment with additional immunosuppressive therapy such as TNF inhibitors (e.g., infliximab at 5 mg/kg every 2 weeks' dose) started. Caution: rule out sepsis and refer to infliximab label for general guidance before using infliximab. – Once the patient is improving, gradually taper steroids over ≥ 28 days and consider prophylactic antibiotics, antifungals, and, in particular, anti-PJP treatment (refer to current NCCN guidelines for treatment of cancer-related infections [Category 2B recommendation]).^a
Diarrhea/Colitis	Any Grade	General Guidance	For Any Grade: 
 – Monitor for symptoms that may be related to diarrhea/enterocolitis (abdominal pain, cramping, or changes in bowel habits such as increased frequency over baseline or blood in stool) or related to bowel perforation (such as sepsis, peritoneal signs, and ileus). – Patients should be thoroughly evaluated to rule out any alternative etiology (e.g., disease progression,

Specific Immune-Mediated Reactions

Adverse Events	Severity Grade of the Event (NCI CTCAE version5.0)	Dose Modifications	Toxicity Management
			
other medications, or infections), including testing for clostridium difficile toxin, etc.
 
 – Steroids should be considered in the absence of clear alternative etiology, even for low-grade events, in order to prevent potential progression to higher grade event. – Use analgesics carefully; they can mask symptoms of perforation and peritonitis.

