			
 – If still no improvement within 3 to 5 days despite 2 to 4 mg/kg IV methylprednisolone, promptly start immunosuppressives such as infliximab at 5 mg/kg once every 2 weeks^a. Caution: it is important to rule out bowel perforation and refer to infliximab label for general guidance before using infliximab. – Consider, as necessary, discussing with study physician if no resolution to Grade ≤ 1 in 3 to 4 days. – Once the patient is improving, gradually taper steroids over ≥ 28 days and consider prophylactic antibiotics, antifungals, and anti-PJP treatment (refer to current NCCN guidelines for treatment of cancer-related infections [Category 2B recommendation]).^a
Grade 3 or 4 (Grade 3 diarrhea: stool frequency of ≥ 7 over baseline per day; hospitalization indicated; severe increase in ostomy compared to baseline; limiting self care ADL Grade 4 diarrhea: life threatening consequences; urgent intervention indicated) (Grade 3 colitis: severe abdominal pain, peritoneal signs; Grade 4 colitis: life-threatening	Grade 3 Permanently discontinue study drug/study regimen for Grade 3 if toxicity does not improve to Grade ≤ 1 within 14 days; study drug/study regimen can be resumed after completion of steroid taper. Grade 4 Permanently discontinue study drug/study regimen.		For Grade 3 or 4: 
 – Promptly initiate empiric IV methylprednisolone 2 to 4 mg/kg/day or equivalent. – Monitor stool frequency and volume and maintain hydration. – Urgent GI consult and imaging and/or colonoscopy as appropriate. – If still no improvement within 3 to 5 days of IV methylprednisolone 2 to 4 mg/kg/day or equivalent, promptly start further immunosuppressives (e.g., infliximab at 5 mg/kg once every 2 weeks). Caution: Ensure GI consult to rule out bowel perforation and refer to infliximab label for general guidance before using infliximab. – Once the patient is improving, gradually taper steroids over ≥ 28 days and consider prophylactic antibiotics, antifungals, and anti-PJP treatment (refer to current NCCN guidelines for treatment of cancer-related infections [Category 2B recommendation]).^a

Specific Immune-Mediated Reactions

Adverse Events	Severity Grade of the Event (NCI CTCAE version5.0)	Dose Modifications	Toxicity Management
	consequences, urgent intervention indicated)		
Hepatitis (elevated LFTs)	Any Grade	General Guidance	For Any Grade:

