			
 – Promptly initiate empiric IV methylprednisolone at 1 to 4 mg/kg/day or equivalent. – If still no improvement within 3 to 5 days despite 1 to 4 mg/kg/day methylprednisolone IV or equivalent, promptly start treatment with immunosuppressive therapy (i.e., mycophenolate mofetil). Discuss with study physician if mycophenolate is not available. Infliximab should NOT be used. – Perform hepatology consult, abdominal workup, and imaging as appropriate. – Once the patient is improving, gradually taper steroids over ≥ 28 days and consider prophylactic antibiotics, antifungals, and anti-PJP treatment (refer to current NCCN guidelines for treatment of cancer-related infections [Category 2B recommendation]).^a
Grade 3 or 4	For Grade 3:	For Grade 4:	
(Grade 3:)	For elevations in transaminases $\leq 8 \times$ ULN, or elevations in bilirubin $\leq 5 \times$ ULN:	(Grade 4:)	
	
 • Hold study drug/study regimen dose until resolution to Grade ≤ 1 or baseline • Resume study drug/study regimen if elevations downgrade to Grade ≤ 1 or baseline within 14 days and after completion of steroid taper. • Permanently discontinue study drug/study regimen if the elevations do not downgrade to Grade ≤ 1 or baseline within 14 days 		
	For elevations in transaminases $> 8 \times$ ULN or elevations in bilirubin $> 5 \times$ ULN, discontinue study drug/study regimen.		
	Permanently discontinue study drug/study regimen for any case meeting Hy's law criteria (AST and/or ALT $> 3 \times$ ULN + bilirubin $> 2 \times$ ULN without initial findings of cholestasis (i.e., elevated alkaline P04) and in the absence of any alternative cause. ^b		
		For Grade 4:	
		Permanently discontinue	

Specific Immune-Mediated Reactions

Adverse Events	Severity Grade of the Event (NCI CTCAE version5.0)	Dose Modifications	Toxicity Management
study drug/study regimen.			

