	Grade 2, 3 or 4 (Grade 2: Symptoms with mild to moderate activity or exertion) (Grade 3: Severe with symptoms at rest or with minimal activity or exertion; intervention indicated; new onset of symptoms) (Grade 4: Life-threatening consequences; urgent intervention indicated (e.g., continuous IV therapy or mechanical	
 - If Grade 2 -- Hold study drug/study regimen dose until resolution to Grade 0. If toxicity rapidly improves to Grade 0, then the decision to reinitiate study drug/study regimen will be based upon treating physician's clinical judgment and after completion of steroid taper. If toxicity does not rapidly improve, permanently discontinue study drug/study regimen. - If Grade 3-4, permanently discontinue study 	For Grade 2-4: 
 - Monitor symptoms daily, hospitalize. - Promptly start IV methylprednisolone 2 to 4 mg/kg/day or equivalent after Cardiology consultation has determined whether and when to complete diagnostic procedures including a cardiac biopsy. - Supportive care (e.g., oxygen). - If no improvement within 3 to 5 days despite IV methylprednisolone at 2 to 4 mg/kg/day, promptly start immunosuppressive therapy such as TNF inhibitors (e.g., infliximab at 5 mg/kg every 2 weeks). Caution: It is important to rule out sepsis and refer to infliximab label for general guidance before using infliximab. - Once the patient is improving, gradually taper steroids over ≥ 28 days and consider prophylactic antibiotics, antifungals, or anti-PJP treatment (refer to current NCCN

Specific Immune-Mediated Reactions

Adverse Events	Severity Grade of the Event (NCI CTCAE version5.0)	Dose Modifications	Toxicity Management
	hemodynamic support))	drug/study regimen.	guidelines for treatment of cancer-related infections [Category 2B recommendation]). ^a

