13.3.2 Interim Analyses for Toxicity

Under the same model described for futility, toxicities will be monitored assuming a prior probability of toxicity following $\text{Beta}(0.6, 1.4)$ in the current treatment arm against a constant rate of 0.30. Based on a previous study, we assume that a 15% rate of toxicity events would be acceptable and a 30% rate of toxicity would be unacceptable. [68] For trial monitoring and decisions about future trials, extreme toxicities (TOX) will be defined as any grade 3 or higher adverse event that is possibly, probably, or definitely related to any therapy received on this protocol and occur between the first dose of Durvalumab and surgery (or 4 weeks after that dose if the patient does not receive surgery as scheduled) with the following exception. Any grade 3 adverse event that is

potentially treatable with steroids will only count as an extreme toxicity if it does not improve to grade 2 or better within 2 weeks. Grade 3 nausea or vomiting that responds to anti-emetics within 72 hours and asymptomatic grade 3 or 4 lipase or amylase elevations will not count as TOX. The trial will be terminated if $\text{Prob}(\Theta_{\text{TOX}} > 0.30 | \text{data}) > 0.9$, where Θ_{TOX} is the proportion of patients experiencing a TOX event. Following this rule, the trial will be terminated according to the following table once the first 3 patients are evaluable.

If there are this many patients (or more) with TOX	3	4	5	6	7	8	9	10	11
Stop the cohort if there are this many (or fewer) patients who are evaluable (have TOX or completed 4 weeks after first Durvalumab dose without TOX)	3	7	9	12	14	17*	20	22	25*

* Always stop with 25 patients in Cohort A, but if 11 or more patients have TOX, then this treatment regimen is too toxic for further use. Always stop at 15 patients in Cohorts B and C, but if 8 or more patients have TOX, then this regimen is too toxic for further use.

Three patients in each cohort will be accrued first. If 3 of the 3 patients have TOX, stop that cohort and the treatment will be declared as too toxic for that cohort. If there is at least 1 patient with surgery without TOX, the next patient will be entered in the study, unless the trial needs to stop according to futility boundaries above. Check continuously as described above for toxicity assuming the trial does not stop for futility first. The operating characteristics for the combined futility and toxicity are summarized in the following table

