13.3.3 Interim Analyses for Toxicity Post Surgery Immune-therapy

Under the same model described for futility and toxicity above, toxicities on immune-therapy after surgery will be monitored assuming an a priori probability of toxicity following Beta(0.4,1.6) in the current treatment against a constant rate of 0.20. For trial monitoring and decisions about future trials, extreme toxicities (TOXpost) will be defined as any grade 3 or higher adverse event that is possibly, probably, or definitely related to any therapy received on this protocol and occur after surgery between the first dose of adjuvant immune-therapy and the final dose received (up to 12 weeks) with the following exception. Any grade 3 adverse event that is potentially treatable with steroids will only count as an extreme toxicity if it does not improve to grade 2 or better within 2 weeks. Grade 3 nausea or vomiting that responds to anti-emetics within 72 hours and asymptomatic grade 3 or 4 lipase or amylase elevations will not count as TOXpost. The trial will be terminated if $\text{Prob}(\text{TOXpost} > 0.20 \mid \text{data}) > 0.9$. Following this rule, the trial will be terminated according to the following table once the first 3 patients are evaluable.

If there are this many patients (or more) with TOXpost	2	3	4	5	6	7	8
Stop the cohort if there are this many (or fewer) patients who are evaluable (have TOXpost or completed 4 weeks after first adjuvant immune-therapy dose without TOXpost)	3	6	9	13	17	21	25*

* Only patients who successfully have surgery and begin treatment with immune-therapy will be included. The table goes to 25 patients as the maximum of possible patients.

Three patients in each cohort will be accrued first. If 2 of the 3 patients have TOXpost, stop this portion of the trial and the adjuvant treatment will be declared as too toxic for this population. Check continuously as described above for toxicity. The operating characteristics (OCs) for this stopping rule for are summarized in the following table assuming all 25 or 15 patients in each cohort receive surgery and start adjuvant immune-therapy. Since we do not expect all 25 or 15 patients to enter this portion of the study, the OCs are slightly over-estimated.

		Stop if $\text{Prob}(\text{TOXpost} > 0.20 \mid \text{data}) > 0.90$					
		Cohort A (N=25)			Cohorts B and C (N=15)		

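### The post-surgery toxicity rule closes its event window at the last dose received, so read literally it does not count toxicity that ends adjuvant treatment

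*Combined protocol and SAP*

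**What the plan says.** Section 13.3.3 monitors toxicity of the adjuvant immunotherapy with a Beta(0.4, 1.6) prior against a constant 0.20. It stops a cohort when the posterior probability of exceeding 0.20 is above 0.9, starting at 3 evaluable patients. A TOXpost event is a grade 3 or higher event, at least possibly related to protocol therapy, that must "occur after surgery between the first dose of adjuvant immune-therapy and the final dose received (up to 12 weeks". A grade 3 event that steroids might treat "will only count as an extreme toxicity if it does not improve to grade 2 or better within 2 weeks".

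A patient joins the denominator on having TOXpost or on having "completed 4 weeks after first adjuvant immune-therapy dose without TOXpost".

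The pre-operative rule in Section 13.3.2 closes differently. It counts events "between the first dose of Durvalumab and surgery (or 4 weeks after that dose if the patient does not receive surgery as scheduled".

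Table 7.7.1 in Section 7.7 sets out when immune-mediated events end dosing. Section 7.4.1 collects adverse events to 90 days after the last post-operative durvalumab dose, and Section 13.4 tabulates them.

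**The concern.** The window closes at the dose actually received. When toxicity stops treatment, the last dose has already been given, so the event that caused the stop comes after the window has shut. The patient is then added at 4 weeks as evaluable without TOXpost, which lowers the posterior probability.

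Safety of the post-operative treatment is part of the primary objective (Section 1.1), and 13.3.3 is the only quantitative stopping rule for it. The same definition is meant to inform decisions about later trials. The prospective weight lies with cohorts B and C, since Section 13.2 expects cohort A to be about full when the revision is approved.

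**Working it through.** **1. The plan's own figures.** With t events in n evaluable patients the posterior is Beta(0.4 + t, 1.6 + n − t); stop if P(rate > 0.20) > 0.90. At the seven printed boundaries:

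| Events / evaluable | 2/3 | 3/6 | 4/9 | 5/13 | 6/17 | 7/21 | 8/25 |
|---|---|---|---|---|---|---|---|
| Posterior | 0.907 | 0.914 | 0.925 | 0.913 | 0.907 | 0.904 | 0.903 |

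One more event-free patient brings each to between 0.846 and 0.895, so all seven boundaries are reproduced. Exact binomial recursion, looking after every patient from n = 3 to N − 1, gives Pr(stop early):

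| True rate | N=25 printed | N=25 recomputed | N=15 printed | N=15 recomputed |
|---|---|---|---|---|
| 0.05 | 0.01 | 0.009 | 0.01 | 0.009 |
| 0.10 | 0.04 | 0.042 | 0.04 | 0.040 |
| 0.20 | 0.25 | 0.251 | 0.20 | 0.200 |
| 0.30 | 0.62 | 0.617 | 0.47 | 0.467 |
| 0.40 | 0.89 | 0.888 | 0.73 | 0.732 |

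The arithmetic is sound. The gap is in which events feed it.

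**2. Which events the literal window leaves out.** Set the TOXpost definition beside Table 7.7.1:

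- Grade 3 diarrhea/colitis: "Permanently discontinue study drug/study regimen for Grade 3 if toxicity does not improve to Grade" 1 or lower within 14 days. Grade 3 hepatitis: "Permanently discontinue study drug/study regimen if the elevations do not downgrade to Grade" 1 or lower, or baseline, within 14 days. A steroid-treatable grade 3 event is TOXpost only if still above grade 2 at 2 weeks. A colitis that meets that criterion therefore also meets the condition for ending treatment, and so does a hepatitis unless it is back to baseline.
- Grade 4 colitis and hepatitis end dosing.
- Grade 3 or 4 pneumonitis: "Permanently discontinue study drug/study regimen". The same applies to grade 3 or 4 nephritis. For myocarditis: "If Grade 3-4, permanently discontinue study" treatment.
- A related death between infusions also comes after the final dose.

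Still counted are events with onset on a dosing day and events after which dosing resumes within the window. Some endocrine events are of the second kind, because the table allows dosing to resume or continue.

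**3. Worked example under the literal reading.** Two of the first 3 adjuvant patients have a related grade 4 event on day 10 after the first dose and get no further dose.

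- Both counted: Beta(0.4 + 2, 1.6 + 1) = Beta(2.4, 2.6), P(rate > 0.20) = 0.907, above 0.90: stop.
- Neither counted: Beta(0.4 + 0, 1.6 + 3) = Beta(0.4, 4.6), P(rate > 0.20) = 0.126: continue.

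**4. The other reading of the 12 weeks.** Suppose the parenthesis means 12 weeks from the first dose whether or not dosing continues. The day-10 events then count. On a four-weekly schedule, doses fall at weeks 1, 5, 9 and 13 (Table 10.2 for cohort A; the four-weekly interval in Section 5.1 for cohort C). The fourth dose is 13 − 1 = 12 weeks after the first, so the window closes on about the day it is given and later events are still not counted.

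**5. Effect on stopping, as illustration.** The documents do not give the share of qualifying events outside the window. Assume a share m, so that counted rate = true rate × (1 − m). Pr(stop early), N=25 / N=15:

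| True rate | m = 0 | m = 10% | m = 25% | m = 50% |
|---|---|---|---|---|
| 0.30 | 0.617 / 0.467 | 0.505 / 0.382 | 0.336 / 0.261 | 0.119 / 0.103 |
| 0.40 | 0.888 / 0.732 | 0.803 / 0.634 | 0.617 / 0.467 | 0.251 / 0.200 |

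The m = 25% entry at 0.40 can be read from the plan's own table: 0.40 × 0.75 = 0.30, printed as 0.62 / 0.47.

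**The case against.** The strongest reply is that the example uses the reading least friendly to the plan. For a patient given one dose, the 4-week evaluability clause makes sense only if events in those weeks can count, and the 12 weeks may run from the first dose. This has force as evidence of intent. But the clause sets the denominator and does not extend the event window, and the 12-week reading still loses events after the fourth dose. Two careful readers can count the same patient differently, which a stopping rule should not allow.

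Second, other oversight exists. Events are collected to 90 days, serious ones are reported, and toxicity summaries go for review and approval. Under Section 7.6.2, a transaminase rise above 3 × ULN with bilirubin above 2 × ULN that is unexplained or attributed to study drug leads to a cumulative review that can interrupt dosing or entry. All of that stands, so a reader who inferred that these events escape notice would be wrong. None of it feeds the boundary.

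Third, the pre-operative rule is a weak precedent. That phase has a single dosing occasion, so its window has to run past the dose. I accept this; the point does not depend on it.

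Fourth, a reader might infer from four months of two-weekly oleclumab and the week-15 column of Table 10.3 that cohort B dosing outruns the 12-week cap. The documents do not support that. The oleclumab row as extracted has seven marks, which fits weeks 1 to 13, and the same four-month description is used for cohort C, whose four-weekly doses end at week 13.

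**Conclusion.** The point holds. As written, 13.3.3 leaves out treatment-ending toxicity and death between infusions, and on either reading of the 12 weeks it leaves out events after a completed four-weekly course. Under the literal reading this can reverse a decision at the first look (0.126 against 0.907), with no assumed rate needed.

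The loss in stopping probability is not known. The fall from 0.89 / 0.73 to 0.62 / 0.47 rests on an assumed 25% missed share at a true rate of 0.40 and on all 25 or 15 patients starting adjuvant immunotherapy, as in the printed table. It should not be read as an estimate. Nor are the printed operating characteristics wrong: they are correct for the rate of counted events, and describe the true toxicity rate only if every qualifying event is counted.

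**What to change.** Redefine the window in 13.3.3: TOXpost is any qualifying event, including death, from the first adjuvant immunotherapy dose through a stated fixed period after the last adjuvant dose received, whether or not further doses follow. The length is for the sponsor to set; 28 days is one example. Then state that:

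- a patient counted as evaluable at 4 weeks without TOXpost is changed to TOXpost if an event occurs later in the window (Section 13.4 already updates futility status in this way, to week eight);
- the 0.20 limit, the prior and the operating characteristics refer to this window, with the sponsor confirming that 0.20 suits it.

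The boundaries, and the treatment-stopping criteria in Table 7.7.1, stay as they are.

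The cost is a few sentences plus matching follow-up. The 30-day toxicity contact in Tables 10.2 and 10.3 has a margin of 2 weeks, so it can fall on day 30 − 14 = 16, before a 28-day window closes. It may be by phone, which would not detect a laboratory abnormality, so its timing and content need checking. Final status comes later. The rule will also stop more often, as the printed characteristics already imply. If half the events were being missed at a true rate of 0.20 (counted rate 0.10), Pr(stop early) would rise from 0.04 / 0.04 to the printed 0.25 / 0.20.

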13.3 Interim Monitoring

A Bayesian sequential monitoring design[66, 67] will be used to monitor the trial for surgery and toxicity rates. Generally, interim analyses will begin after 3 patients become evaluable, and will then be performed continuously to ensure that patients are exhibiting reasonable toxicity and surgery rates to continue the trial. Specific rules are in each subsection below. Since 1-2 patients are expected to be enrolled each month, monitoring data will be kept up-to-date and the tables below checked prior to consenting each patient once the 3rd patient in each cohort has been on study 4 weeks after the first dose of Durvalumab. Enrollment will not need to wait for the previous patient to become evaluable, but the rules will be checked for all evaluable patients before consenting each patient. This includes a risk of 1-2 patients entering on the study beyond the designed stopping rules, which is considered a reasonable risk. If accrual occurs faster than 1-2 patients per month, this practice will be reconsidered. All calculations for stopping boundaries and operating characteristics were performed in Multicenter Lean Desktop v2.1.

Patients will be evaluable once they have received the first dose of Durvalumab/tremelimumab, durvalumab/oleclumab or durvalumab/monalizumab and have then had 8 weeks time to go to surgery. If surgery has not occurred by 8 weeks then for monitoring these patients will have been considered not to have gone to surgery even if they do after 8 weeks. Patients will be allowed up to 12 weeks to complete surgical resection. If surgical resection is not done within 12 weeks from then patient will be removed from clinical trial

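### In 13.3.3 the post-surgery toxicity rule waits for a third evaluable patient after 2 of 2 have TOXpost, although its own criterion is already met: a small safety inefficiency with a one-sentence fix

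*Combined protocol and SAP*

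**What the plan says.** Section 13.3.3 monitors TOXpost with a Beta(0.4, 1.6) prior against a constant rate of 0.20 and a posterior cutoff of 0.90. The sentence before the boundary table says that "the trial will be terminated according to the following table once the first 3 patients are evaluable". The first table column pairs 2 TOXpost with 3 patients, under the row heading "Stop the cohort if there are this many (or fewer) patients who are evaluable". Below the table the minimum is repeated: "Three patients in each cohort will be accrued first. If 2 of the 3 patients have TOXpost, stop this portion of the trial". Section 13.3 states it for the monitoring as a whole: "Generally, interim analyses will begin after 3 patients become evaluable".

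Timing also matters. TOXpost can occur at any time from the first to the last adjuvant dose, up to 12 weeks. A patient without an event becomes evaluable on having "completed 4 weeks after first adjuvant immune-therapy dose without TOXpost". A grade 3 event that steroids might treat "will only count as an extreme toxicity if it does not improve to grade 2 or better within 2 weeks". The tables are checked before each consent (13.3). Summary reports follow the first three evaluable patients and then every 2 to 4 (13.4).

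**The concern.** A minimum number of patients before the first look normally guards against an early fluke that the next patient could reverse. That reason is missing here. Once two adjuvant patients are evaluable and both have TOXpost, the criterion is met, and no single further result brings the posterior back under the cutoff. The text still withholds the action until a third patient is evaluable.

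During the wait another resected patient may start the regimen, or one already on it may continue. Section 5.1 lets these patients have chemotherapy instead, so a prompt stop leaves them an alternative.

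**Working it through.** **Inputs (13.3.3).** Prior Beta(0.4, 1.6); reference rate 0.20; cutoff 0.90; first look at 3 evaluable; maximum 25 (cohort A) or 15 (cohorts B and C).

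**Formula.** With x TOXpost among n evaluable, Pr(rate > 0.20) = 1 − F(0.20), where F is the Beta(0.4 + x, 1.6 + n − x) distribution function. Stop if this exceeds 0.90.

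**The plan's own figures.** The formula reproduces all seven boundaries (2/3, 3/6, 4/9, 5/13, 6/17, 7/21, 8/25). An exact recursion looks after each patient from n = 3 and does not count a crossing at the maximum as early. It matches the printed operating characteristics. At rates 0.05, 0.10, 0.20, 0.30 and 0.40, Pr(stop early) is 0.009, 0.042, 0.251, 0.617 and 0.888 for N = 25, and 0.009, 0.040, 0.200, 0.467 and 0.732 for N = 15.

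**The state in question.**

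| Data | Posterior | Pr(rate > 0.20) | Action |
|---|---|---|---|
| 2 of 2 | Beta(2.4, 1.6) | 0.957 | stop criterion met |
| 2 of 3 | Beta(2.4, 2.6) | 0.907 | stop |
| 3 of 3 | Beta(3.4, 1.6) | 0.990 | stop |
| 2 of 4 | Beta(2.4, 3.6) | 0.846 | no stop |

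**Is the wait in the printed figures?** Yes. At a true rate of 0.40 the printed means are 9.9 and 8.3. A first look at n = 3 gives 9.94 and 8.26; a first look at n = 2 gives 9.78 and 8.10.

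**Effect in the one-at-a-time model.** The first two patients both have TOXpost with probability p²: 0.20² = 4%, 0.30² = 9%, 0.40² = 16%. Every such path also stops at n = 3. A look at n = 2 therefore leaves Pr(stop early) unchanged and saves one patient on those paths, so mean N falls by exactly p².

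**Effect in calendar time.** The documents do not give the share of patients who start adjuvant immunotherapy or the timing of TOXpost, so this part rests on assumptions: accrual of 1–2 a month as Poisson, 40–80% starting, surgery at 3–10 weeks, adjuvant start 4–12 weeks later, TOXpost uniform over 12 weeks, a counting lag of 0 or 2 weeks, and enrollment with or without 5-patient blocks. Simulating 200,000 cohorts of 15 per setting gave:

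| True rate | Cohorts reaching exactly 2 evaluable, both TOXpost | Avoidable adjuvant starts per cohort |
|---|---|---|
| 0.20 | 1.3–3.5% | 0.01–0.03 |
| 0.30 | 2.9–7.8% | 0.03–0.08 |
| 0.40 | 5.1–13.9% | 0.05–0.14 |

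These percentages fall below p² because another patient is often evaluable at 4 weeks before the second event is counted. They are not upper limits. If every TOXpost fell within 4 weeks, the state would occur in 4.4–6.4%, 9.7–13.7% and 17.1–22.9% of cohorts.

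**Other rules.** The pre-operative TOX rule uses Beta(0.6, 1.4) against 0.30. There 2 of 2 gives 0.928, but 2 of 3 gives 0.838, so the third patient can reverse the stop. For futility, 0 of 2 gives 0.9003, barely over the cutoff, and the printed table does not stop at 1 surgery in 3. Waiting for three is informative in both.

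**The case against.** The strongest reply is that the three-patient minimum is a disclosed choice. It is stated in 13.3, repeated in each rule and built into the printed operating characteristics. The effect is small, and patients have other protection: holding or stopping drug for individual events (7.7) and serious adverse event reporting (7.5). All of this stands and keeps the point minor. The overrun of 1–2 patients accepted in 13.3 has a different cause, though: "Enrollment will not need to wait for the previous patient to become evaluable". That is delay in learning outcomes. Here the outcomes are known and the action is held back.

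A reader might infer four stronger things that the documents do not support.

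- *The boundary is wrong.* It is not; every entry follows from the stated prior and cutoff.
- *The table heading contradicts the text.* Its wording would cover 2 of 2 on its own, but the preceding sentence says when the table begins to apply, so the two can be read together. It is at most an ambiguity.
- *After 2 of 2 a stop is certain.* It is certain only if a check falls at exactly three evaluable patients. With checks at consents and reports every 2 to 4 evaluable patients, the next look may be at 2 of 4 (0.846, no stop), or no third patient may arrive.
- *The fix never adds a stop.* That holds in the one-at-a-time model only. A small simulation with checks only at consent (6,000 cohorts per setting, the same 12-week assumptions, 5-patient blocks, no lag) suggested about 0.2–0.6 percentage points more stops at a true rate of 0.20. This is a small downside, and it also shows that the wait can lose a stop the criterion had reached.

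**Conclusion.** The point holds for one state only: exactly two evaluable adjuvant patients in a cohort, both with TOXpost. Section 13.3.3 then withholds a stop that its own criterion supports and that the third result alone could not reverse. It is a small safety inefficiency, not a boundary error.

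The posteriors and the p² figures follow from the plan's inputs and are firm. The count of avoidable starts depends on the assumed start rates and timing and is only an order of magnitude. The reach is mainly cohorts B and C, because 13.2 expected cohort A to have about 25 patients enrolled when this revision was approved. Minor; a cheap improvement.

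**What to change.** In 13.3.3, after the sentence that introduces the table, add: *If the only two evaluable adjuvant patients in a cohort both have TOXpost, the stopping action is taken at once, without waiting for a third evaluable patient.* Keep the three-patient minimum for the pre-operative TOX and futility rules.

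The cost is one sentence and five printed means. For N = 25, 24.2 becomes 24.1, 15.2 becomes 15.1 and 9.9 becomes 9.8 (rates 0.10, 0.30, 0.40). For N = 15, 10.8 becomes 10.7 and 8.3 becomes 8.1 (rates 0.30, 0.40). Printed Pr(stop early), medians and quartiles stay as they are.
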